10.4.5 Guidelines for reporting adverse events of special interest

For AESIs, the Sponsor must be informed immediately (ie, within 24 hours), as per SAE notification guidelines described in [Section 10.4.4](#), even if not fulfilling a seriousness criterion, using the corresponding screens in the e-CRF.

Instructions for AE reporting are summarized in [Table 3](#).

10.4.6 Guidelines for management of specific laboratory abnormalities

A decision tree for the management of laboratory abnormalities suggestive of vasculitis (including but not limited to hematuria, proteinuria, increased ESR and/or hsCRP, etc) is provided in [Appendix H](#).

Decision trees for the management of certain laboratory abnormalities by Sanofi are provided in [Appendix K](#).

The following laboratory abnormalities should be monitored, documented, and managed according to the related flow chart in protocol appendices.

- Neutropenia
- Thrombocytopenia
- Increase in ALT
- Acute renal insufficiency
- Suspicion of rhabdomyolysis

NOTE: However, if a seriousness criterion is met, the Sponsor is informed immediately (ie, within 1 working day) using the corresponding screens in the e-CRF, following the same process as described for the SAEs.

Table 3 - Summary of adverse event reporting instructions

Event category	Reporting timeframe	Specific events in this category	Case Report Form completion		
			AE form	Safety Complementary Form	Other specific forms
Adverse Event (non-SAE, non-AESI)	Routine	Any AE that is not SAE or AESI	Yes	No	No
Serious Adverse Event	Expedited (within 24 hours)	Any AE meeting seriousness criterion per Section 10.4.1.2	Yes	Yes	No
Serious Adverse Event AESI	Expedited (within 24 hours)	Any AE meeting seriousness criterion per Section 10.4.1.2	Yes	Yes	As applicable
Adverse Event of Special Interest	Expedited (within 24 hours)	Pregnancy	Yes	Yes	No
		Symptomatic overdose	Yes	Yes	No
		ALT >3 x ULN	Yes	Yes	Yes
		[REDACTED]	[REDACTED]	[REDACTED]	[REDACTED]
		Anaphylactic reactions or acute allergic reactions	Yes	Yes	Yes
		Severe injection site reactions	Yes	Yes	Yes
		TB or initiation of medications for suspected TB	Yes	Yes	Yes
		Acute renal failure	Yes	Yes	No

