10.4.4 Instructions for reporting serious adverse events

In the case of occurrence of an SAE, the Investigator or any designees must immediately:

- ENTER (within 24 hours) the information related to the SAE in the appropriate screens of the e-CRF; the system will automatically send a notification to the monitoring team after approval of the Investigator within the e-CRF or after a standard delay.
- SEND (preferably by fax or e-mail) a photocopy of all examinations carried out and the dates on which these examinations were performed, to the representative of the monitoring team whose name, fax number, and email address appear on the clinical trial protocol. Care should be taken to ensure that the patient's identity is protected and the patient's identifiers in the clinical trial are properly mentioned on any copy of a source document provided to the Sponsor. For laboratory results, include the laboratory normal ranges.
- All further data updates should be recorded in the e-CRF as appropriate, and further documentation as well as additional information (for laboratory data, concomitant medications, patient status, etc) should be sent (by fax or e-mail) to the monitoring team within 24 hours of knowledge of the SAE. In addition, every effort should be made to further document any SAE that is fatal or life-threatening within a week (7 days) of the initial notification.
- A back-up plan (using a paper CRF process) is available and should be used when the e-CRF system does not work.

Any SAE brought to the attention of the Investigator at any time after the end of the study for the patient and considered by him/her to be caused by the IMP with a reasonable possibility, should be reported to the monitoring team.

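### The note in Protocol 10.4.6 gives serious laboratory abnormalities a limit of 1 working day, in conflict with the 24-hour SAE process it refers to, the AESI rule and Table 3

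*Protocol*

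**What the plan says.** Protocol 10.4.6 lists neutropenia, thrombocytopenia, ALT increase, acute renal insufficiency and suspected rhabdomyolysis, to be handled by the flow charts in the appendices. A note below the list adds that "if a seriousness criterion is met, the Sponsor is informed immediately (ie, within 1 working day"), through the e-CRF and "following the same process as described for the SAEs".

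The other reporting rules are:

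- **10.4.4 (SAEs):** the investigator must "ENTER (within 24 hours) the information related to the SAE in the appropriate screens of the e-CRF". Further documentation "should be sent (by fax or e-mail) to the monitoring team within 24 hours of knowledge of the SAE".
- **10.4.5 (AESIs):** "For AESIs, the Sponsor must be informed immediately (ie, within 24 hours"), whether or not the event is serious.
- **Table 3, directly under the note:** the rows for SAEs, serious AESIs and AESIs all read "Expedited (within 24 hours"). The SAE row covers "Any AE meeting seriousness criterion per Section 10.4.1.2".

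The SAP does not deal with reporting times.

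**The concern.** Sections 10.4.5 and 10.4.6 stand next to each other and explain the same word, immediately, by two different limits. The note applies only once a seriousness criterion is met. Under 10.4.3 a laboratory abnormality that meets one is recorded as an AE, and it is then an SAE. No separate class of event is left for a longer limit to govern.

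The literal result is also the wrong way round. ALT above 3 x ULN and acute renal failure are AESIs under 10.4.1.3, so their non-serious forms are due in 24 hours. Section 10.4.1.2 counts ALT above 3 x ULN with bilirubin above 2 x ULN as medically important, hence serious. On the wording of the note alone, that more serious event has the longer limit.

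What is at stake is when the Sponsor hears of the event. Section 10.4.6 is where sites are sent for these abnormalities, so staff may well look up the deadline there. The Sponsor's expedited reporting under 10.5 cannot begin before it has been told. A site and a monitor could also apply different limits to the same report, each citing the protocol.

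**Working it through.** No sample size, power or error rate is involved, and the plan states no delay figure to reproduce. The check compares the limits and then works out how far apart they are.

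**1. Which limit applies to which event**

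| Event | Note in 10.4.6 | Elsewhere in the protocol |
|---|---|---|
| Serious neutropenia, thrombocytopenia, suspected rhabdomyolysis | 1 working day | 24 h (10.4.4; Table 3, SAE row) |
| Serious ALT increase, serious acute renal failure | 1 working day | 24 h (10.4.4; 10.4.5 where also an AESI; Table 3) |
| Non-serious ALT above 3 x ULN, non-serious acute renal failure | not covered | 24 h (10.4.5; Table 3, AESI rows) |

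The 10.4.6 list says renal insufficiency, while 10.4.1.3 and Appendix K say renal failure. I treat these as one event, because both sections send the reader to the appendix flow charts and Appendix K has only one for it.

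**2. Size of the gap**

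Assumptions, none of which the documents settle: working days are Monday to Friday, there is no public holiday, and both clocks start when the site learns of the event.

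Excess = (deadline under 1 working day) − (time of awareness + 24 h).

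On the plain reading, the deadline is the same clock time on the next working day:

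- Monday to Thursday: 24 − 24 = 0 h.
- Friday (due Monday): 72 − 24 = 48 h.
- Saturday (due Monday): 48 − 24 = 24 h.
- Sunday (due Monday): 24 − 24 = 0 h.

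Two other readings were tried, with awareness times from 00:00 to 23:00. Excess in hours:

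| Awareness | Same clock time, next working day | 17:00, next working day | Weekend clock starts Monday 09:00 |
|---|---|---|---|
| Monday to Thursday | 0 | −6 to 17 | 0 |
| Friday | 48 | 42 to 65 | 48 |
| Saturday | 24 | 18 to 41 | 34 to 57 |
| Sunday | 0 | −6 to 17 | 10 to 33 |

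For example, with the 17:00 deadline, Friday 00:00 to Monday 17:00 is 89 h, and 89 − 24 = 65 h. With the Monday start, Saturday 09:00 runs to Tuesday 09:00, and 72 − 24 = 48 h. A negative value means that the working-day limit falls before the 24-hour one.

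A Monday holiday adds 24 h to the plain Friday case: 96 − 24 = 72 h.

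**3. After the change**

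With 24 hours in the note, the excess is 0 h on every day and all four places agree.

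**The case against.** The strongest reply is that the note does not create a separate rule. It says immediately, routes the event into the SAE process, and stands directly above a table that gives 24 hours for anything serious. A site that follows the cross-reference reports within 24 hours. On the plain reading that also satisfies the note, since the excess is never negative. ALT above 3 x ULN and acute renal failure carry their own 24-hour AESI limit as well.

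Much of this stands. The note is an ambiguous, conflicting limit and not a clear waiver, and the controlling rule can be found in three other places. But the cross-reference does not remove the conflict: one sentence states a limit of 1 working day and points to a process with a limit of 24 hours.

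A reader might go on to infer more than the documents support:

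- **That safety review, the DMC or stopping decisions are delayed.** The limits govern what the site enters and sends. No clock is set for the Sponsor's review. The DMC reviews data periodically (9.2) under a charter that is not among the documents. Section 10.3.3 ties discontinuation for laboratory abnormalities to a recheck and the Appendix K algorithms, and nothing there makes it wait for the Sponsor to be notified.
- **That reporting compliance cannot be judged.** It can be judged against 10.4.4 and Table 3, which cover every SAE. The difficulty is that a second standard is also in print.
- **That weekend events in general arrive two days late.** On the plain reading, 48 h belongs to Friday awareness. Saturday gives 24 h and Sunday none.

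**Conclusion.** The inconsistency is real and stands in current text. The 10.4.6 note contradicts the process it cites, the AESI rule and Table 3, and taken literally it ranks serious ALT and renal events behind their non-serious forms.

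Its size is bounded. On the plain reading of a Monday-to-Friday week, notification of the Sponsor could come 0 to 48 h later than the 24-hour rule allows, with the maximum for Friday awareness. The largest excess on the other readings tried is 65 h, and a public holiday would add to these figures. All of them rest on an assumed definition of working day and on a site that relies on the note alone.

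This is a wording conflict in a safety-reporting rule that should be corrected. It affects no endpoint, population, efficacy analysis or error rate, and it supports no conclusion about DMC review or stopping of treatment.

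**What to change.** In the note in Protocol 10.4.6, replace the limit of 1 working day by 24 hours, and keep the reference to the SAE process. The note then matches 10.4.4, 10.4.5 and Table 3, and working day no longer needs a definition there. The cost is one phrase in a protocol amendment or a letter to sites. No new form, procedure or SAP change is needed.

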10.5 OBLIGATIONS OF THE SPONSOR

During the course of the study, the Sponsor will report in an expedited manner:

- All SAEs that are both unexpected and at least reasonably related to the IMP (SUSAR), to the regulatory authorities, Independent Ethics Committee/ Institutional Review Board (IECs/IRBs) as appropriate and to the Investigators.

- All SAEs that are expected and at least reasonably related to the IMPs to the regulatory authorities, according to local regulations.

Adverse events that are considered expected will be specified by the reference safety information (IB).

Unblinding of SUSARs by the Sponsor is described in this section.

[figure not shown]
In this study, progression of the underlying condition is anticipated and thus will be considered as expected for the purpose of regulatory reporting. Please refer to the IB.

[figure not shown]
Any other AE not listed as an expected event in the IB or in this protocol will be considered unexpected.

For regulatory purposes, the treatment code will be unblinded at Sponsor Pharmacovigilance department level for reporting to the Health Authorities of any suspected unexpected adverse drug reaction (SUSAR) and reasonably associated with the use of the IMP according to either the judgment of the Investigator and/or the Sponsor. Apart from Sponsor Pharmacovigilance department, within the company and associated organizations, the results of this unblinding should remain undisclosed.

The Sponsor will report all safety observations made during the conduct of the trial in the clinical study report and in the development safety update report.

10.6 Safety instructions

10.6.2 Tolerability at the IMP injection

10.6.2.1 Local injection site reactions

Local injection site reactions that are considered as non-allergic events should be further characterized and evaluated with the assessment of the severity grading of related symptoms such as corresponding for pain, tenderness, erythema/redness, swelling, itching or other (See [Appendix J](#)). Special e-CRF screens will need to be completed. If such an AE were to occur, then do not report the individual components of the reaction but rather the term "local injection site reaction", the individual components being described in the specific e-CRF screen.

10.6.3 Systemic allergy reaction

10.6.3.1 Anaphylaxis

Allergic reaction is a potential risk associated with the administration of most therapeutic monoclonal antibodies.

Acute allergic reactions may be defined as allergic reaction-mediated signs and symptoms experienced by patients during or shortly after the pharmacologic or biologic agent is given.

These reactions may present in a variety of ways, including dizziness, headache, anxiety, dyspnea, hypotension, tachycardia, pruritus, rash, urticarial/angioedema, flushing, nausea, or vomiting.

Anaphylaxis may represent the most severe form of an allergic reaction. Allergic reactions may begin within few hours and persist up to 24 hours post dosing. Refer to [Appendix I](#) "Definition of anaphylaxis", which describes the clinical criteria for the diagnosis of anaphylaxis.

Patients should be monitored by site personnel or visiting nurse (if injection is performed at the patient's home) for at least 30 minutes or up to 2 hours as per country specific requirements after each administration of investigational product for any signs or symptoms of a hypersensitivity reaction.

Patients should be treated as medically appropriate if any AEs are observed. General Allergic Reaction and/or Local Injection Site Reaction Complementary Form will have to be completed.

Sometimes transient injection site reactions, irritant in nature, may occur, requiring no intervention and being of dubious significance. These reactions would not be considered to be allergic reactions, and should only be recorded on the Local Injection Site Reaction Complementary Form.

The IMP should be temporarily discontinued immediately if there is a suspicion of an allergic event related to IMP. Refer to [Section 10.4.1.3](#) for hypersensitivity reactions to be reported as AESIs, and to [Section 10.3](#) for hypersensitivity reactions requiring permanent treatment discontinuation.

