	
• Tolerability at the IMP injection site:
- Erythema/redness (diameter and graded severity)- Swelling/induration/edema (diameter and graded severity)- Pain assessment. 
Immunogenicity:
 
• Testing for ADA 
Pharmacokinetics:
 
• SAR156597 plasma concentrations 
Biomarkers:
 
• Measurement of protein biomarkers associated with the activity of the disease (COMP, CCL2) and the IL-4/IL-13 pathway (TARC, periostin, and eotaxin-3).• Archived blood samples for future assays of protein and mRNA biomarkers related to the disease and the response to therapy (requires separate informed consent).
ASSESSMENT SCHEDULE	
The study will comprise 8 on-site visits AND 4 phone calls:
 
• Visits:
- V1 (screening visit) between Day -28 and Day -1.- V2 (baseline visit) at Day 1 (first dosing).- Treatment period: V3 at Week 2, V4 at Week 4, V5 at Week 8, V6 at Week 12, V7 at Week 24.- V8 (End-of-Study [EOS] visit) at Week 35.- A time window of ± 2 days will be allowed for each visit.• Phone calls:
- For safety considerations phone calls will be made at Week 6, 16 and 20 during the treatment period, and at Week 30 during the follow-up period.

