- l* In women of child-bearing potential. After Visit 6 (W12) and until subsequent study visit the patient will have a urine pregnancy test at home on a monthly basis. Patients will be given sufficient urine pregnancy kits to take home for monthly testing up until the end-of-study visit. When the testing coincides with a study visit as indicated in the flow chart, the results should be reported in the e-CRF. When the testing is done at home between study visits, the results should be collected by the Investigator during the monthly phone calls (Week 16 and Week 20) and reported in the electronic case report form (e-CRF). If any interim urine pregnancy test performed by the patient is positive, the patient should immediately report to the investigator for appropriate follow-up and pregnancy reporting as appropriate
- m* Local tolerability of SC injections will be assessed by the study nurse either at patient's place or at the site for the inter-visit SC injection given once a week. One patient booklet to record information on injections administered at home will be provided to the patient at baseline and will be reviewed at each visit by Investigator
- n* Step 1 of CRISS will be assessed based upon available data and individual components of Step 2 of CRISS will be captured through other efficacy procedures (eg, Change in mRSS, HAQ-DI, patient and physician global assessments and FVC)
- o* This will be assessed using a Likert scale for CRISS calculations and will be a separate assessment from the global assessment conducted for the SHAQ using a VAS.
- p* This will be assessed using a Likert scale for CRISS calculations.
- q* Health care resources will include hospitalizations (reason, number of days per hospital admission, date of entry, date of discharge from hospital), number of out-patients visits by type (gastroenterologist, pulmonologist, occupational therapist, psychiatrist, physiotherapist, other), sick leaves (number of day off from work) and caregiver support (time spent per day to take care of the patient, number of days off from work to take care of the patient)
- r* An additional IVRS call will need to be made at Week 18 for IMP dispensation. Only 6 weeks of IMP will be dispensed with the IVRS call made at Visit 6 (W12)

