 - Perform Pulmonary function tests (PFTs): observed and % predicted FVC and observed and % predicted Carbon Monoxide DLco (corrected for hemoglobin).

- Dispense and administer IMP
 - Patients will be monitored for at least 30 minutes or up to 2 hours as per country specific requirements after dosing for any signs or symptoms of a hypersensitivity reaction. An assessment of local tolerability at the injection site (present pain, erythema/redness, swelling/induration/edema and other related observations) will be conducted
 - Provide the patient with a booklet to record information pertaining to the injections to be performed at home at Week 1 as well as the treatment kit
- Schedule an appointment for Visit 3

10.1.3 Visit 3: on treatment/Week 2

- Record all concomitant medication use
- Inquire about AEs/SAEs
- Review patient booklet to assess local tolerability at the injection site and treatment compliance
- Record vital signs including BP, heart rate and weight

Perform a complete physical examination (Refer to [Section 9.2.2.1](#))

- Call IVRS to dispense a 2 week treatment kit allocation
- Administer IMP for Week 2
 - Patients will be monitored for at least 30 minutes or up to 2 hours as per country specific requirements after dosing for any signs or symptoms of a hypersensitivity reaction. An assessment of local tolerability at the injection site (present pain, erythema/redness, swelling/induration/edema and other related observations) will be conducted
- Provide treatment kit to be administered at Week 3
- Schedule an appointment for Visit 4

10.1.4 Visit 4: on treatment/Week 4

- Questionnaires/forms to be completed:
 - SHAQ (by patient)
 - UCLA SCTC GIT 2.0 (by patient)
 - Patient Global Assessment (by patient)
 - Physician Global Assessment (by Investigator)
- Record all concomitant medication use
- Inquire about AEs/SAEs

- Review patient booklet to assess local tolerability at the injection site and treatment compliance
- Record vital signs including BP, heart rate and weight
- Perform a complete physical examination (Refer to [Section 9.2.2.1](#)), including:
 - Perform the mRSS
 - Perform a TJC28
 - Perform a digital ulcer count
- Perform 12-lead ECG
- Blood and Urine Testing
 - Obtain blood samples for complete clinical laboratory determinations including hematology and biochemistry profile
 - Obtain urine for urinalysis (dipstick)
 - Perform urine pregnancy test for women of childbearing potential

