10.4.3 General guidelines for reporting adverse events

- All AEs, regardless of seriousness or relationship to IMP, spanning from the signature of the informed consent form until the end of the study as defined by the protocol for that patient, are to be recorded on the corresponding screen(s) of the e-CRF.
- Whenever possible, diagnosis or single syndrome should be reported instead of symptoms. The Investigator should specify the date of onset, intensity, action taken with respect to IMP, corrective treatment/therapy given, additional investigations performed, outcome, and his/her opinion as to whether there is a reasonable possibility that the AE was caused by the IMP or by the study procedure(s).
- The Investigator should take appropriate measures to follow all AEs until clinical recovery is complete and laboratory results have returned to normal, or until progression has been stabilized, or until death, in order to ensure the safety of the patients. This may imply that observations will continue beyond the last planned visit per protocol, and that additional investigations may be requested by the monitoring team up to as noticed by the Sponsor.
- When treatment is prematurely discontinued, the patient's observations will continue until the end of the study as defined by the protocol for that patient.
- Laboratory, vital signs or ECG abnormalities are to be recorded as AEs only if:
 - Symptomatic and/or
 - Requiring either corrective treatment or consultation, and/or
 - Leading to IMP discontinuation or modification of dosing, and/or
 - Fulfilling a seriousness criterion, and/or
 - Defined as an AESI

Instructions for AE reporting are summarized in [Table 3](#).

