Appendix J Assessment of Local Injection Site Reactions

Reaction to Injectable Product	Mild (Grade 1)	Moderate (Grade 2)	Severe (Grade 3)	Very Severe (Grade 4)
Pain	Does not interfere with activity	Interferes with activity or repeated use of non-narcotic pain reliever	Prevents daily activity or repeated use of narcotic pain reliever	Emergency Room (ER) visit or hospitalization
Tenderness	Mild pain to touch	Pain with movement	Significant pain at rest	ER visit or hospitalization
Erythema / Redness *	2.5 – 5 cm	5.1 – 10 cm	>10 cm	Necrosis or exfoliative dermatitis
Swelling **	2.5 – 5 cm and does not interfere with activity	5.1 – 10 cm or interferes with activity	> 10 cm or prevents daily activity	Necrosis
Itching	Does not interfere with activity	Interferes with activity or repeated use of topical or systemic treatment	Prevents daily activity or leads to other significant dermatologic conditions (such as infection, scarring, etc.)	ER visit or hospitalization
Other (Please specify)***	No modification of daily activities and/or does not require symptomatic treatment.	Hinders normal daily activities and/or requires symptomatic treatment.	Prevents daily activities and requires symptomatic treatment.	ER visit or hospitalization

* In addition to grading the measured local reaction at the greatest single diameter, the measurement should be recorded as a continuous variable.

[figure not shown]
** Swelling should be evaluated and graded using the functional scale as well as the actual measurement.

*** Please specify the other signs or symptoms (for example, hematoma, discoloration, re-activation, etc).

ADAPTED from the toxicity grading scale table from the FDA Draft Guidance for Industry: Toxicity Grading Scale for Healthy Adult and Adolescent Volunteers Enrolled in Preventive Vaccine Clinical Trials April 2005

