2.1.5 Safety endpoints

The safety analysis will be based on the reported adverse events and other safety information, such as clinical laboratory data, vital signs, ECG.

Observation period

The observation period will be divided into 4 epochs:

- The **pre-treatment** epoch is defined as the time from the signed informed consent date up to the first administration of IMP.
- The **treatment** epoch is defined as the time from the first administration of the IMP to the last administration of the IMP + 7 days.
- The **residual treatment** epoch is defined as the time from the last administration of the IMP + 8 days to the last administration of the IMP + 84 days.

The treatment-emergent adverse event (TEAE) period will include both **treatment** and **residual treatment** epochs.

- The **post-treatment** epoch is defined as the period of time starting the day after the end of the TEAE period up to the end of the study (defined as last protocol-planned visit or last study assessment).

The on-study observation period is defined as the time from the first administration of IMP until the end of the study (defined as last protocol planned visit or last study assessment).

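### Injection-site tolerability is a listed safety endpoint with no planned analysis, and conflicting recording rules may leave transient reactions out of the adverse event tables

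*Protocol*

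**What the plan says.** **Endpoint.** The protocol synopsis, under safety endpoints, lists "Tolerability at the IMP injection site": erythema and swelling, each by diameter and graded severity, and a pain assessment.

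**Collection.** At dosing visits from Visit 2 (Protocol 10.1.2) to Visit 6 (10.1.7), the post-dose procedures include "An assessment of local tolerability at the injection site". For the weekly injections between visits, the flow chart footnote (Protocol 1.2) states: "Local tolerability of SC injections will be assessed by the study nurse". Appendix J sets four grades for pain, tenderness, erythema, swelling, itching and other signs. For the greatest diameter it adds that "the measurement should be recorded as a continuous variable".

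**Recording.** Four places bear on where a local reaction is recorded:
- Protocol 10.4.3 sends to the e-CRF "All AEs, regardless of seriousness or relationship to IMP".
- Protocol 10.6.2.1 has a non-allergic local reaction reported under a single AE term, with its components on a specific e-CRF screen.
- Protocol Table 3 assigns the AE form, and neither a complementary nor another specific form, to an AE that is neither serious nor of special interest.
- Protocol 10.6.3.1 says transient irritant reactions that need no intervention "should only be recorded on the Local Injection Site Reaction Complementary Form".

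**Analysis.** SAP 2.1.5 states: "The safety analysis will be based on the reported adverse events and other safety information, such as clinical laboratory data, vital signs, ECG". SAP 2.4.5.1 to 2.4.5.5 cover AEs, deaths, laboratory variables, vital signs and ECG. The safety part of SAP Appendix B lists AEs, vital signs, laboratory variables and ECG. Protocol 11.4.3 has the same scope, with a section on liver injury.

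**The concern.** A listed safety endpoint is measured at every dose and then used in no planned output. Without a stated variable, denominator and table, the trial can follow its SAP exactly and still not report how well the injection was tolerated locally.

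Injection-site reactions would then be seen only through AE-page data, in the general TEAE tables and the severe-reaction AESI. The recording rules do not agree on whether a transient reaction reaches the AE page. Two sites, each following a different section, could record the same reaction differently. The injection-site rows of the TEAE tables would then partly reflect how sites read the protocol.

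**Working it through.** **1. Amount of data.** Dosing is weekly from Day 1 with the last dose at Week 23, so 24 doses per patient. Planned patients: 94. Planned injections: 24 × 94 = 2,256. This counts planned assessments only and says nothing about bias.

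**2. Outputs that could use the data.**

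| Output | Source | Uses diameter, Appendix J grade, pain or the Complementary Form? |
|---|---|---|
| TEAE tables (SAP 2.4.5.1) | AE page | No |
| Severe-reaction AESI (SAP 2.1.5.1) | AE coding (high-level term) and AE intensity | No |
| Laboratory, vital signs, ECG (SAP 2.4.5.3 to 2.4.5.5) | Their own data | No |
| SAP Appendix B, safety part | AEs, vital signs, laboratory, ECG | No |

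**3. The AESI and Appendix J use different scales.** Protocol 10.4.1.3 defines the severe-reaction AESI by reference to Appendix J. There, erythema above 10 cm is Grade 3 (severe) whatever its effect on function. The SAP selects on AE intensity, and Protocol 10.4.1.1 makes an AE severe when it prevents daily activities and needs corrective or symptomatic treatment. A patient with erythema above 10 cm who carries on as usual is severe on the first scale and need not be on the second.

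**4. Recording rules side by side.** Protocol 10.4.3, 10.6.2.1 and Table 3 point to an AE entry. Protocol 10.6.3.1, on its plain reading, points to the form alone. It does not mention the AE page.

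**5. What form-only recording would do.** The documents state no reaction rate, so there is no plan figure to reproduce and the values here are assumed. Let *p* be the share of patients with any injection-site reaction, and *s* the share of those patients whose reactions were all recorded on the form only. The tabulated rate is *p*(1 − *s*).

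For *p* from 10% to 40% and *s* from 25% to 75%, it runs from 10% × 0.25 = 2.5% to 40% × 0.75 = 30%.

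With assumed true rates of 30% (active) and 10% (placebo), and the same *s* in both arms:

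| *s* | Active | Placebo | Risk difference | Risk ratio |
|---|---|---|---|---|
| 0% | 30% | 10% | 20 points | 3.0 |
| 25% | 22.5% | 7.5% | 15 points | 3.0 |
| 50% | 15% | 5% | 10 points | 3.0 |
| 75% | 7.5% | 2.5% | 5 points | 3.0 |

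The first row is what results if sites also make an AE entry. With equal *s*, the absolute rates and their difference shrink and the ratio does not change.

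**The case against.** The strongest reply concerns the word *only* in Protocol 10.6.3.1. The sentence sits in a section on systemic allergy, shortly after one saying that a "General Allergic Reaction and/or Local Injection Site Reaction Complementary Form will have to be completed". The sentence that follows may therefore mean only that a transient irritant reaction does not belong on the allergy form. With Protocol 10.6.2.1 supplying an AE term for local reactions, nothing need be lost from the TEAE tables. How the form links to the AE page depends on e-CRF instructions that are not in these documents. This reply stands against any claim that understatement is certain.

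Second, SAP 2.1.5 gives examples and not a closed list, and Protocol 10.5 commits the sponsor to report all safety observations in the study report. That is true, but neither place names a variable, population, denominator or table.

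Third, physical examination is also a listed safety endpoint without its own SAP table; Protocol 9.2.2.1 turns significant post-screening findings into AEs. Local tolerability differs: it has its own grading scale, a measured diameter and a form, and one section appears to keep some reactions on that form.

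A reader might infer that the reported injection-site reaction rate will be too low, and more so in the arm with more mild reactions. The documents do not support that. It needs sites to apply the form-only reading, and it needs such reactions to occur. If the form-only share is equal across arms, the relative comparison is unchanged. The severe-reaction AESI should not be affected by this recording rule either, because reactions needing no intervention would not be severe.

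**Conclusion.** The analysis gap is firm and depends on no assumption. A listed safety endpoint, assessed at about 2,256 planned injections, has no planned output in Protocol 11.4.3 or the SAP, and the one injection-site-specific output does not use the grade by which the protocol defines it.

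The conflict between recording rules is also firm. Its effect on the TEAE tables is conditional: wherever sites record transient reactions on the form only, those reactions will be missing; wherever sites also make an AE entry, there is no understatement. The documents give no rate from which to size it, and zero is possible.

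The primary efficacy result is untouched and safety is descriptive. The change should still be made, because following the plan as written can leave a listed endpoint unreported.

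**What to change.** 1. In SAP 2.1.5, 2.4.5 and Appendix B, add local tolerability as a safety variable. By arm, summarise the number and percentage of patients, and of injections, with erythema, swelling and pain, by maximum Appendix J grade and by diameter. State the denominator: injections given or injections assessed.
2. Report injection-site reaction incidence from any source (AE page or Complementary Form), and show how it relates to the TEAE counts. The grade table will also show how many reactions reached the Appendix J severe grades, which can be set against the AESI count.
3. Reconcile Protocol 10.4.3, Table 3, 10.6.2.1 and 10.6.3.1, so that every site records a transient local reaction in the same way.

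Cost: one or two descriptive tables, a listing and SAP wording, from data the protocol already collects. This assumes that the booklet and form entries reach the database. The reported reaction rate may become less favourable.
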